Aim 1. Characterize the acute analgesic effects of alcohol in individuals with chronic temporomandibular joint and muscle disorder (TMD). Despite evidence that self-medication of pain with alcohol is common among people with TMD (Riley and King, 2009), quantitative data regarding the magnitude of this effect is largely lacking. Similarly, it is unclear whether the acute analgesic effects of alcohol may differ between individuals with and without chronic pain. We believe TMD is an ideal model with which to test the acute effects of alcohol intake on clinical pain because it is a relatively common condition (~5-12% of the general population; Goulet et al., 1995; Johansson et al., 2006), and clinically relevant pain can be reliably evoked in laboratory settings by applying pressure at the insertion of the masseter muscle (i.e., pressure algometry; Brown et al., 2000). **Hypothesis (H)1.** We hypothesize that consumption of a dose of alcohol sufficient to produce a breath alcohol concentration (BrAC) of ~ .08 g/dL will be associated with significant reduction in pain sensitivity compared to placebo in both TMD patients and healthy controls, and **H2.** acute alcohol will be associated with greater ratings of perceived relief than placebo following pain induction. Evidence from the animal literature suggests chronic pain may modulate the acute effects of opioid administration. Furthermore, chronic pain is associated with maladaptive plasticity in brain regions that underpin acute alcohol effects, including medial prefrontal cortex and nucleus accumbens (for review, see Egli et al., 2012). Thus, although it is likely that TMD patients may experience differential effects of alcohol use on pain sensation compared to healthy controls, the directionality of this effect is currently unclear. Thus, we predict **H3.** chronic pain status will moderate the magnitude of alcohol analgesia but ask as an empirical question **(E)1.** whether the effect of alcohol on pain sensitivity will be stronger or weaker in this group. Attenuated analgesic response in TMD patients would be consistent with rat studies suggesting neuropathic pain shifts opioid dose-response curves, increasing opioid self-administration (Egli et al., 2012). In contrast, an

exaggerated analgesic response would suggest alcohol use might be especially negatively reinforcing.

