Aim 2. Determine the influence of typical alcohol use and expectation of pain relief with alcohol use on magnitude of alcohol analgesia and associated feelings of relief. Studies of alcohol analgesia in healthy adults have indicated that individual patterns of typical alcohol use, motivation to drink, and personality factors may modulate alcohol analgesia, suggesting a critical role of conditioning and expectancies (Brown and Cutter, 1977; Cutter et al., 1979; Ralevski et al., 2010). However, this question has never been directly examined, either in healthy adults or those with chronic pain. **H4.** We predict individuals with stronger positive expectancies regarding alcohol analgesia will have significantly stronger analgesic responses to alcohol administration. **H5.** Based on previous research, we predict that individuals who endorse greater and more frequent alcohol consumption will experience a greater analgesic effect of alcohol, independent of the effect of expectancies. Finally, we ask as **E2.** whether chronic pain status will be associated with stronger expectancies of pain relief following alcohol consumption and **E3.** greater ratings of pain relief during pressure algometry after drinking.

6. Research Plan:

General Approach. For this study of current non-problem drinkers, we propose a repeated-measures, double blind placebo-controlled factorial design with chronic pain status (TMD vs. healthy control) as a between-subjects factor and alcohol administration (Alcohol Dose: placebo, 0.08 g/dL) as a within-subjects factor. The study will include both men and women. Study procedures will occur at the Center for Pain Research and Behavioral Health of the University of Florida under supervision of the PI (JB).

Methods

Participants. Individuals seeking care for temporomandibular joint and muscle disorder (TMD) (n=25) will be recruited for the study via flyers, word of mouth, internet/local radio advertisements, and [name] orthodontic clinic. A sample of healthy social drinkers without TMD (HC) will also be recruited as a comparison group (n=25). Individuals aged 21-45 years will be recruited to avoid any vulnerability to acute neurobehavioral effects of alcohol associated with older age (e.g., [name] et al., 2016a). Because TMD is more prevalent in women than men (~2:1; Campbell et al., 2017), we anticipate the final sample will consist of approximately 2/3 women.

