Selection Criteria. TMD diagnosis will be confirmed by [name], a practicing orthodontist and orofacial pain expert, or a qualified dentist designated by [name] in situations where he may not be available, based on published Research Diagnostic Criteria (Schiffman et al., 2014). As guided by the Research Diagnostic Criteria for TMD, TMD participants in the TMD group must report TMD-related orofacial pain over the 6 months preceding screening. Participants will be excluded if they have a history of a chronic pain condition other than TMD (e.g., osteo- or rheumatoid arthritis, fibromyalgia, complex regional pain syndrome); report use of opioid analgesics; current

major depression; history of any psychotic disorder; undercontrolled hypertension or diabetes

(as reflected by self-report); neurological disease (e.g., multiple sclerosis, epilepsy, amyotrophic lateral sclerosis, Parkinson's disease); serious medical illness (e.g., hepatitis, HIV/AIDS); impaired cognitive function; or history of drug or alcohol dependence. Because chronic smoking is associated with adverse neurobehavioral changes ([name] et al., 2011; Durazzo et al., 2013), participants must be non-smokers. Participants must also be current drinkers (i.e., consume at least 1 drink/month over the last 6 months). Alcohol abstinent or naïve individuals will be excluded. To avoid confounding effects of binge-drinking patterns, participants must score lower than an 8 on the AUDIT. To increase ecological validity and ensure feasibility of recruitment, use of prescription medications will be allowed provided they do not contraindicate alcohol use ([name] et al., 2014; Gilbertson et al., 2009).

Screening Measure	Domain	Exclusionary Cutoff
BDI-II	Depressive Symptomology	≥ 20 (moderate depression)
STAI	State/Trait Anxiety	Not Exclusionary
AEQ	Alcohol Expectancies	Not Exclusionary
AUQ	Alcohol Use Pattern	Not Exclusionary
AUDIT	Alcohol Use Disorder Sx	≥ 8
PILL	Somatic preoccupation /neuroticism	Not Exclusionary
FTQ	FH Assessment	Not Exclusionary
PSQI	Sleep Quality	Not Exclusionary
BRS	Resilience to stressors	Not Exclusionary
DIS	Ability to tolerate physical discomfort	Not Exclusionary
EAA	Expectancies regarding pain relief from alcohol	Not Exclusionary
PCS	Pain catastrophizing	Not Exclusionary
PASS-20	Pain-related Anxiety	Not Exclusionary
IRI	Empathy	Not Exclusionary
OHIP-TMD	TMD Pain Severity and Interference	Not Exclusionary

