
Data Analysis Strategy. Data will be analyzed using SPSS 24 (IBM Corp., Armonk, NY).

Aim 1. Determine the effect of chronic pain status on magnitude of alcohol analgesia and associated feelings of relief. To assess hypotheses and empirical questions related to Aim 1, chronic pain status will be included as an independent variable in repeated measures general linear models analyses (rmGLM; SPSS GLM procedure; repeated: dose), with QST measures, associated relief ratings, and SEAS measures as dependent variables. Demographic, personality/affective (i.e., BDI/STAI/IRQ/BFI), substance use-related (recent alcohol use/alcohol use disorder symptomatology), pain-related (TMD severity), and biological (i.e., approximated menstrual phase for female participants) variables will be included as covariates should any correlate significantly with magnitude of alcohol analgesia or relief ratings.

Aim 2. Determine the influence of typical alcohol use, and alcohol analgesia-related expectancies on magnitude of alcohol analgesia and associated feelings of relief. A combination of approaches will be used to address Aim 2. Simultaneous multiple regression of alcohol analgesia expectancy and typical alcohol consumption

(estimated in ounces of absolute ethanol consumed per day derived from the AUQ) on QST measures will be used to evaluate H4 and H5. As in Aim 1, rmGLM will be used to assess E2 and E3.

Power Analysis. Power analyses for the proposed work are based on effect sizes derived from our initial feasibility study (see attached grant application for details) and were performed assuming two-tailed hypothesis tests with alpha=.05. Effect sizes are reported as Cohen's d, Pearson's r, or R2 (Cohen, 1988). Analyses indicated N=50 would provide excellent (98%) power to detect analgesic effects of alcohol administration on QST measures (Cohen's d > .58) and correlations between VAS ratings of relief and alcohol analgesia (r = .64). Critically, this sample size will also provide 80% power to detect small-to-medium sized effects (d > .40; r > .37; R² > .14) for which prior estimates are not available (e.g., the effect of chronic pain status on alcohol analgesia and subject alcohol affects). *We will recruit a total of 60 qualified subjects over the course of the project to account for 10% anticipated participant dropout before completing all study visits.*

7. Possible Discomforts and Risks:

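### TMD severity can be selected into the Aim 1 model beside chronic pain status, which costs the H3 test power and, if severity matters within group, changes what it estimates

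*Combined protocol and SAP*

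**What the plan says.** All references are to the combined protocol and SAP.

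- **H3** (section 5, Aim 1) predicts that "chronic pain status will moderate the magnitude of alcohol analgesia". In a two-dose crossover this is the group-by-dose term. E1 leaves the direction open.
- **Model** (section 6, Data Analysis Strategy, Aim 1): "chronic pain status will be included as an independent variable in repeated measures general linear models analyses", with dose as the repeated factor, in the SPSS GLM procedure.
- **Covariates** (same paragraph): the candidates include "pain-related (TMD severity), and biological (i.e., approximated menstrual phase for female participants". The entry rule is that such "variables will be included as covariates should any correlate significantly with magnitude of alcohol analgesia or relief ratings".
- **Groups** (section 6, Participants and Selection Criteria): "TMD participants in the TMD group must report TMD-related orofacial pain over the 6 months preceding screening". For the other arm, "A sample of healthy social drinkers without TMD (HC) will also be recruited as a comparison group". The planned sizes are 25 and 25.
- **Severity measure** (Table 1): OHIP-TMD, described as "TMD Pain Severity and Interference". Screening Procedure collects the Table 1 measures without restricting any of them to one group.
- **Power Analysis**: 80% power is stated at d of .40 for effects "for which prior estimates are not available (e.g., the effect of chronic pain status on alcohol analgesia and subject alcohol affects".

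No section confines severity to the TMD group, names an H3 model without it, or says whether the entry correlation is pooled or computed within group.

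**The concern.** Severity of TMD is close to a graded version of the group factor. If it is scored in everyone, patients score higher than controls. A pooled correlation between severity and analgesia can then be significant for no reason other than a real group difference. So the rule is most likely to bring severity in when H3 is true.

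In a repeated-measures GLM a between-subject covariate is fitted at each dose level, so severity is crossed with dose. Group-by-dose then compares a patient with a control of equal TMD severity. Two consequences follow:

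- If severity has no within-group relation to analgesia, the expected coefficient stays the same but its standard error grows.
- If severity does have such a relation, the coefficient estimates a different quantity from the overall difference between people with and without chronic TMD pain.

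A named Aim 1 hypothesis would then be judged on a weaker or altered test, chosen by screening the same outcome.

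**Working it through.** **1. The plan's own figures.** With N=50 and two-sided alpha .05, a paired noncentral-t calculation gives 98.0% at d=.58 (stated 98%) and 79.2% at d=.40 (stated 80%). For the group effect the 80% depends on how d is read:

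- As f = .40/2 = .20 with an assumed between-session correlation of .5, power is 79.1%. The noncentrality is .20² × 50 × 2/(1 − .5) = 8. Setting 12.5δ² = 8 gives a difference in change of δ = 0.80 SD.
- As a between-group d of .40 on the change score, 25 v 25 gives 28%.

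The difference with 80% unadjusted power at 25 v 25 is 0.81 SD, which almost equals the first reading. It is the reference below.

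**2. Set-up.** With two dose levels, group-by-dose is the group coefficient in a regression on the alcohol-minus-placebo difference. Severity enters if its pooled Pearson correlation with one analgesia score has p<.05, that is |r|>.279 at N=50. Simulations used 40,000 trials per cell. The total group difference was held fixed and the within-group outcome SD set to 1.

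The documents give no severity distribution. The severity-group correlation r is therefore assumed at .4, .5, .7, .8 and .9, under two spreads:

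- **Equal spread:** mean gap = 2r/√(1−r²), in TMD-group SDs.
- **Controls vary little** (control SD 0.2 of the TMD SD): the same expression times √((1+0.04)/2) = 0.721.

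**3. No within-group slope.** When severity enters, the standard error is multiplied by 1/√(1−r²). The expected coefficient stays at 0.81. Results for the two spreads agree within about 1 point.

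| r | .4 | .5 | .7 | .8 | .9 |
|---|---|---|---|---|---|
| SE multiplier | 1.09 | 1.15 | 1.40 | 1.67 | 2.29 |
| Severity selected, 0.81 SD | 18% | 26% | 48% | 60% | 70% |
| Power after the rule, 0.81 SD (80% without) | 76% | 72% | 58% | 45% | 27% |
| Power after the rule, d=.40 on change (28% without) | 26% | 25% | 19% | 16% | 11% |

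**4. Slope 0.3 SD of outcome per TMD-group SD of severity, same direction as the group effect.** Adjusted difference = 0.81 − 0.3 × gap. For example, at r=.7 with equal spread, 0.81 − 0.3 × 1.96 = 0.22.

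| r | .4 | .5 | .7 | .8 | .9 |
|---|---|---|---|---|---|
| Gap, equal spread | 0.87 | 1.15 | 1.96 | 2.67 | 4.13 |
| Adjusted difference | 0.55 | 0.46 | 0.22 | 0.01 | −0.43 |
| Correct-direction power | 46% | 33% | 9% | 3% | 1% |
| Gap, controls vary little | 0.63 | 0.83 | 1.41 | 1.92 | 2.98 |
| Adjusted difference | 0.62 | 0.56 | 0.39 | 0.23 | −0.08 |
| Correct-direction power | 56% | 44% | 19% | 9% | 3% |

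**5. Slope −0.3, difference 0.81 SD.** Power is 84/83/80/79/75% with equal spread and 81/81/78/74/67% if controls vary little. A material loss appears only at high correlations.

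**6. No total group difference.** H3 is rejected in 2-5% of trials with no slope, in 9-13% with a 0.3 slope and equal spread, and in 5-6% with a 0.3 slope if controls vary little.

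**The case against.** **Every correlation and slope is assumed.** This stands. At r of .4 to .5 with no slope the loss is only 4 to 8 points at 0.81 SD. If the entry correlation were computed within group, severity would not be selected merely because H3 is true. The plan does not say which applies.

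**A reader might infer that once severity enters, H3 is no longer tested at all.** That is too strong. With no within-group slope the expected coefficient is still 0.81 and only precision suffers. The documents give no evidence about the slope.

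**A reader might infer that the rule will reverse a true effect or inflate false positives.** Both appear mainly under equal spread, which is the less plausible case when controls are recruited as free of TMD. The −0.43 also needs an opposing direct group effect, since severity alone would contribute 0.3 × 4.13 = 1.24 of a total held at 0.81. If controls vary little, the adjusted difference is at worst −0.08 and rejection under no difference is 5-6%.

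**A reader might infer that controls have no severity score, so that a pooled model drops all 25.** The text points the other way. OHIP-TMD is a screening measure with no group restriction, whereas Laboratory Sessions says expressly when a question (alcohol use for TMD pain) goes to the TMD group only.

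**The study aims at feasibility and effect-size data.** True, but the group-by-dose estimate is one of those effect sizes, and an adjusted 0.39 or 0.22 is not the 0.81 that later work would need.

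**Conclusion.** The point holds as a defect in the analysis rule. The text directs TMD severity into the model that tests H3 whenever a screening correlation is significant, and no H3 model without severity is protected.

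The size of the harm is conditional. It rests on severity being scored in both groups (the natural reading), on a pooled screen, and on the assumed correlations and slopes:

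- With no within-group slope, the harm is lost power only: small at correlations of .4-.5, large at .7-.9.
- With a slope in the direction of the group effect, the target shrinks and power drops steeply.
- With an opposite slope there is little loss except at high correlations.

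E1 leaves the direction of the group effect open, so the sponsor cannot count on the favourable case.

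The calculation concerns TMD severity alone. It does not support barring every screened covariate from the H3 model, nor any criticism of menstrual phase, which the plan already limits to women. The stated power figures are not shown to be wrong here; they simply take no account of this covariate.

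**What to change.** In Data Analysis Strategy, Aim 1, state that H3 is tested in a model without TMD severity as a covariate. Take severity off the covariate list for that model and specify a secondary analysis relating severity to alcohol analgesia within the TMD group only.

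The cost is plan wording. No participants, visits or measures are added. Severity-adjusted comparisons of patients with controls would no longer be made.

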Mechanisms of Pain. Acute pain is a centrally mediated sensation driven by nociceptive input conducted by A δ and C fibers responding to noxious stimulation or tissue injury in the periphery. An individual's experience of pain is modulated by the activity of a well-characterized set of neural structures involved in the contextualization and evaluation of the nociceptive stimulus, including those involved in sensory, limbic, and executive functions (Apkarian et al., 2005; Clarke and Lawrence, 2013; Craggs et al., 2007; Staud et al., 2008). In a minority of cases (~10-20%), pain persists even after the peripheral healing process is complete. The transition from acute to chronic pain is thought to be reflected by central sensitization (i.e., a generalized increase in pain associated with nociceptive input). Central sensitization is underpinned by marked change at multiple levels, including epigenetic modification of nociceptor-related genes (Bai et al., 2014), modulation of dorsal horn n-methyl d-aspartate receptors (NMDARs; Woolf and Salter, 2000), aberrations in functional measures of brain activity during pain (Hashmi et al., 2013), and psychological factors including anxiety, depression, fear, and catastrophizing (Williams, 2013). Therefore, it is likely that biopsychosocial mechanisms underlying alcohol analgesia as well as its efficacy may differ between individuals in acute pain vs. those with chronic pain conditions.

Pain is, by definition, aversive (International Association for the Study of Pain, 1979). Therefore, the cessation of pain is associated with relief. Although conceptually distinct from typical appetitive rewards like palatable food or drugs of abuse, substantial similarity between neurobehavioral responses to relief and appetitive rewards has been reported (Leknes et al., 2011; Seymour et al., 2005; Tanimoto et al., 2004; Ursu and Carter, 2005). Indeed, appetitive rewards are more reinforcing when simultaneously providing relief (Cabénac, 1979; Leknes et al., 2011). **This is likely due to a synergistic combination of positive and negative reinforcement, suggesting self-medication of pain using alcohol may represent a “double-hit” of reinforcement, increasing risk of developing an alcohol use disorder.**

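### Aim 1 covariates are admitted by their correlation with the outcome, so the H3 model and what it estimates are fixed only after the outcomes are seen, and the estimate can be distorted

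*Combined protocol and SAP*

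**What the plan says.** In section 6, Data Analysis Strategy, Aim 1, "chronic pain status will be included as an independent variable in repeated measures general linear models analyses", with dose as the repeated factor and the QST measures, relief ratings and SEAS scores as outcomes. Demographic variables, BDI, STAI, IRQ and BFI, recent alcohol use and alcohol use disorder symptoms, TMD severity, and approximate menstrual phase "will be included as covariates should any correlate significantly with magnitude of alcohol analgesia or relief ratings". This is the only covariate rule given for Aim 1.

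The section does not say:
- whether the correlation is taken over both groups together or within group;
- what significance threshold applies;
- how many candidates there are;
- whether one covariate set serves every outcome;
- whether the adjusted or the unadjusted model decides H3.

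H3, in section 5, Aim 1, is that "chronic pain status will moderate the magnitude of alcohol analgesia". The same paragraph adds that "the directionality of this effect is currently unclear". The General Approach has "chronic pain status (TMD vs. healthy control) as a between-subjects factor", so group is observed and not randomised.

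**The concern.** The covariates are chosen by significance tests against the quantities being modelled. Suppose H3 is true and a candidate differs between TMD participants and controls. That candidate then correlates with analgesia through group membership alone. It passes a pooled filter most often in samples where it happens to mimic the group effect, and once in the model it takes part of that effect with it.

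Such candidates are plausible here. Section 4, Mechanisms of Pain, ties the move to chronic pain to "psychological factors including anxiety, depression, fear, and catastrophizing", and BDI and STAI are on the list. TMD severity is the extreme case, because it measures the condition that defines the group.

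Two things are at stake. One is the size of the H3 estimate, which is the new between-group question. The other is its meaning. With several QST outcomes (intensity, unpleasantness, aftersensation, slope, intercept, threshold) plus relief and SEAS, H3 could be a total difference for one outcome and an adjusted difference for the next.

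**Working it through.** **Plan's own figures.** Two-sided alpha is .05 and N = 50. As a paired test, d = .58 gives noncentrality .58 × √50 = 4.10 and power 98.0%, matching the stated 98%. At d = .40 the paired test gives .40 × √50 = 2.83 and 79.2%, matching the stated 80%. H3, however, compares 25 with 25. At d = .40 the noncentrality is .40/√(2/25) = 1.41 and power 28%; at d = .80 it is 2.83 and 79%. The gap at d = .40 is a separate matter; it is shown only to set the baseline.

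**Reduction.** With two doses, the group-by-dose term is the group difference in D, the alcohol-minus-placebo score. Adding covariates amounts to regressing D on group and those covariates.

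**Assumptions not in the plan.** D = 0.80 × group + N(0,1). There are ten N(0,1) candidates with no effect on D. Two or four of them (the linked ones) are shifted in one group. A candidate enters if its pooled correlation with D has p < .05.

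| Linked candidates, shift | Rule: mean estimate | Rule: power | Linked variables always entered: power |
|---|---|---|---|
| 2, 0.5 SD | 0.75 | 74% | 72% |
| 2, 0.8 SD | 0.72 | 69% | 64-65% |
| 4, 0.5 SD | 0.73 | 72% | 67% |
| 4, 0.8 SD | 0.68 | 62% | 54-56% |
| 4, 1.0 SD | 0.63 | 52% | 45-47% |

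Repeat runs agree to about 0.01 in the estimate and one to two points in power. Always entering the linked variables averages 0.80 in every row. Two fixed unlinked covariates give 0.80 and 77%. So, for inert candidates, the bias comes from selection.

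**Source of the power loss.** Always entering k linked covariates with shift δ multiplies the variance of the group coefficient by about 1 + kδ²/4. Without covariates, SE = √(2/25) = 0.283 and 0.80/0.283 = 2.83.
- k = 2, δ = 0.5: factor 1.125, SE 0.300, ratio 2.67.
- k = 4, δ = 1.0: factor 2.0, SE 0.400, ratio 2.00.

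That is collinearity with group, and it costs at least as much when the variables are prespecified.

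**Other settings, same framework.**
- *No true interaction, inert candidates:* no bias; rejection 3-5%.
- *One inert candidate, shift 0.8 SD:* 0.80 becomes 0.77.
- *Eight inert candidates, all shifted 0.8 SD:* 0.80 becomes 0.59 (power 79% to 45%), and 0.40 becomes 0.29 (28% to 14%).
- *TMD severity scored 0 in controls, mean 3 SD in TMD:* 0.80 becomes 0.70, SE 0.28 becomes 0.57, power 79% becomes 26%.
- *One candidate, shift 0.8, own slope +0.4:* the total difference is 0.80 + 0.8 × 0.4 = 1.12, and the rule reports 0.80, which is the direct difference.
- *Same, slope −0.4:* the total is 0.80 − 0.32 = 0.48, and the rule averages about 0.62-0.64, further from zero.
- *Filter applied within group:* 0.79-0.80 and 76-78%, so essentially no bias.

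**Chance entry.** With ten independent candidates unrelated to D, the probability that at least one enters is 1 − 0.95¹⁰ = 40% for each outcome.

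**The case against.** A reader might infer that the rule biases H3 toward zero whenever a candidate differs by group. That is too strong. There is no bias when the true interaction is zero. An opposing candidate moves the estimate away from zero relative to the total difference. A candidate that acts in the same direction gives a smaller number that correctly answers a different question. A reader might also blame selection for the lost power, but entering the same linked variables in advance gives slightly less power than the rule does. Both objections stand.

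The size also rests on inputs the plan does not supply. Pooling is the natural reading but is not stated, and a within-group filter removes the bias. Treating all ten candidates as inert is unfavourable to the plan, since its Background and Aim 2 expect drinking pattern and personality to matter. Excluding BDI-II scores of 20 or more and AUDIT scores of 8 or more limits how far the groups can differ on two candidates. At d = .40, the mildest setting only takes the estimate to 0.37 and power from 28% to 26%.

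Finally, group is not randomised, so leaving a real confounder out has a cost. If one candidate (shift 0.8 SD, slope 0.4) drives analgesia and group has no direct effect, a model without it rejects 17-18% of the time, against 5-6% under the rule. This stands as a limit on the remedy. It does not defend letting the outcome choose the model.

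**Conclusion.** The concern holds in a limited form. As written, the rule lets the outcome data decide the H3 model and its estimand, and that decision can differ between outcomes. This follows from the text and needs no simulation.

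Attenuation is conditional. It needs a true group-by-dose effect, a pooled filter, and candidates that differ by group without an effect of their own. Under those conditions, with 2 to 4 of 10 candidates shifted by 0.5 to 1.0 SD, a true 0.80 SD averages 0.63 to 0.75, a loss of 0.05 to 0.17 SD. Where candidates have their own effect, the estimand changes and the estimate can move either way. Type I error is not inflated for inert candidates. The fall in power from about 77% to 52-74% is real, but it comes mainly from having group-linked variables in the model. TMD severity is the clearest hazard, because it nearly duplicates group. The shifts, slopes and number of candidates are assumptions. The change is worth making but is not critical: the abstract gives feasibility and effect-size data as one purpose of the study.

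**What to change.** Replace the correlation rule with a covariate list fixed before unblinding and used unchanged for every Aim 1 outcome.

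- *Deciding model for H3:* age and sex, with a statement that it estimates the total TMD-versus-control difference in alcohol analgesia.
- *One labelled secondary model:* add the affective and alcohol-use variables whatever their correlation with the outcome, and report the result as the covariate-adjusted difference.
- *TMD severity:* TMD-only analyses.
- *Menstrual phase:* women-only analyses.

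The cost is SAP wording, with no new data or participants. Some variance reduction is forgone if an affective or drinking score truly predicts analgesia. The deciding model also does not remove group imbalance in affect or drinking, which is why the adjusted model must be reported beside it.

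### The Aim 2 regression for H4 and H5 leaves out chronic pain status, which the plan itself links to analgesia and possibly to expectancy; adding it is a cheap improvement

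*Combined protocol and SAP*

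**What the plan says.** Section 6, Data Analysis Strategy, Aim 2 specifies "Simultaneous multiple regression of alcohol analgesia expectancy and typical alcohol consumption", the latter "derived from the AUQ) on QST measures will be used to evaluate H4 and H5". Those are the only two predictors. The sentence does not mention pain status as a term, a stratifier or an interaction, and it does not restrict the model to one group. The power statement uses N = 50.

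The Aim 1 paragraph just above does name chronic pain status as an independent variable in its repeated measures models. The phrase in Aim 2 that refers back to Aim 1 carries those models to E2 and E3 only. The conditional covariate rule also sits under Aim 1. It lists "pain-related (TMD severity), and biological" variables among others, but not status.

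In section 5, H3 predicts that "chronic pain status will moderate the magnitude of alcohol analgesia", while noting that "the directionality of this effect is currently unclear". Under Aim 2, E2 asks whether pain status goes with stronger expectancies of relief from alcohol. H4 states that "individuals with stronger positive expectancies regarding alcohol analgesia will have significantly stronger analgesic responses to alcohol administration". H5 expects heavier or more frequent drinkers to show more analgesia, "independent of the effect of expectancies".

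**The concern.** H4 and H5 concern what expectancy and drinking habits contribute to analgesia. In a sample built from two groups, the slope for expectancy combines the association inside each group with the line joining the two group means. If TMD participants differ from controls in expectancy, and status also changes analgesia at a given level of expectancy, the second component is a status effect that the model assigns to expectancy.

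The plan raises both links itself: one as a prediction (H3), the other as an open question (E2). Because the direction of H3 is left open, nobody can say beforehand whether H4 would be overstated or masked. H5 has the same structure. However, both groups must be current drinkers with AUDIT below 8, so there is less room for the groups to differ on consumption.

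**Working it through.** **Inputs from the documents.** 25 TMD and 25 HC (Participants); two-sided alpha .05, N = 50, and 80% power for R² > .14 and r > .37 (Power Analysis). The value r = .37 is used below only as a convenient effect size; the plan gives it as a detectable-effect threshold, not an expected value.

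**Assumed inputs.** The Power Analysis says no prior estimate exists for the effect of pain status on analgesia, and no TMD–HC difference in expectancy is given. Let a be the TMD–HC difference in expectancy and δ the direct effect of status on analgesia, meaning the TMD–HC difference at equal expectancy, both in within-group SD units. I vary both from 0 to .8. Expectancy and consumption are taken as independent within groups, and the outcome as the magnitude of analgesia, as the Aim 2 heading has it.

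**Step 1: the plan's own figure.** For one coefficient with R² = .14, the noncentrality is (.14/.86) × 50 = 8.14. With two predictors (47 residual df) power is 79.8%, which matches the stated 80%. With status as a third predictor (46 df) it is again 79.8% at the same partial R².

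**Step 2: bias of the pooled slope.** With equal groups, p(1 − p) = .25, and

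pooled slope = β + .25·a·δ / (1 + .25·a²),

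where β is the within-group slope. The bias is zero if a = 0 or δ = 0. For a and δ of equal size:

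| Size (SD) | Bias | Pooled slope, β = .37, opposing effects |
|---|---|---|
| .2 | .01/1.01 = .010 | .36 |
| .4 | .04/1.04 = .038 | .33 |
| .5 | .0625/1.0625 = .059 | .31 |
| .8 | .16/1.16 = .138 | .23 |

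**Step 3: effect on the H4 test.** These are simulations of 25 + 25 participants by ordinary least squares, 20,000 to 40,000 samples per cell; repeat runs agree within about a point.

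| Size of a and δ (SD) | Rejection, β = 0, same direction: without / with status | Power, β = .37, opposing: without / with status |
|---|---|---|
| .2 | 5% / 5% | 73% / 75% |
| .4 | 6% / 5% | 66–67% / 75% |
| .5 | 7% / 5% | 61% / 75% |
| .8 | 16% / 5% | 38–39% / 75% |

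With status in the model the mean slope is .37 throughout the right-hand column. By the symmetry of the set-up, the same figures apply to H5 if a is read as a consumption difference.

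**Step 4: one link or none, β = .37.**
- No group differences: about 76% without status, 75% with it.
- Groups differ on expectancy, no direct status effect: slope unbiased; 77% without against 75% with status at .4 SD, and 82% against 75% at .8. Here adding status costs power.
- Direct status effect, no expectancy difference: slope unbiased; 74% without against 75% with status at .4 SD, and 68–69% against 75% at .8. Here adding status gains power.

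The direct effect must be kept apart from the total group difference in analgesia, which is δ + .37a. At a = .4 and δ = −.4 the total is −.4 + .148 = −.252 SD. A scenario with total difference zero is therefore not one with a single link; it contains a direct effect that cancels the path through expectancy.

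**The case against.** **The harm is small at moderate sizes.** This stands for false positives: rejection is 5 to 7% up to .5 SD on both variables. Serious harm needs large differences or opposing effects, and opposing effects are one possibility among several.

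**H3 and E2 are tested anyway.** A reader might infer that nobody could tell status from expectancy in the results. That goes too far, because the Aim 1 model and the E2 analysis report on both links and would alert the reader. But they do not correct the H4 coefficient. The alert is also weak: two independent groups of 25 have only 28% power for a .40 SD difference.

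**H4 and H5 do not mention status.** True. The only independence asked for is H5's, from expectancies, and entering both predictors together supplies that. An unadjusted slope is a legitimate quantity, which is why it should still be reported. That the model is pooled is itself inferred, from a single unrestricted regression and a power statement at N = 50.

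**The covariate rule might be carried over.** The text places it under Aim 1, makes it conditional on a significant correlation, and names TMD severity rather than status.

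**The recruitment ratio.** A reader might infer a further fault from the equal group sizes, since TMD is described as a "relatively common condition (~5-12% of the general population". The documents do not support this: the plan nowhere claims a population-weighted slope.

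**Conclusion.** The omission is real, and adding status is a cheap improvement. As written, the H4 and H5 coefficients are open to bias if status both affects analgesia directly and is related to the predictor. The bias is upward for same-direction effects and downward for opposing ones. A reader might infer that H4 will be falsely confirmed; the documents do not show that, because they give no group differences and leave the direction of H3 open.

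Under the assumed sizes the larger risk is a masked effect. Opposing effects of .4 SD take about 8 to 9 points off power, and effects of .8 SD roughly halve it. At .2 SD the loss is about 2 points. For H5 the likely size is smaller, given the restricted drinking range.

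**What to change.** In the Aim 2 paragraph, add chronic pain status (TMD or HC) as a third predictor, test H4 and H5 on the partial coefficients, and report the model without status as a sensitivity analysis.

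Status is already recorded, so the cost is one degree of freedom. At r = .37 that means about 1 point of power if the groups do not differ. If they differ on expectancy but status has no direct effect on analgesia, it means about 3 points at .4 SD and 7 at .8. H4 and H5 then read as associations within pain-status groups, and the plan should say so.
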